**Background, Rationale and Context**

Mounting evidence indicates that preoperative vital signs measurements can reflect undesired perioperative events. However, we rarely measure patients' vital signs in a thorough manner. We generally take a single snapshot and use those values for judging physiologic fitness for surgery and anesthesia.

The Third Perioperative Quality Initiative has identified that ambulatory measurement is the optimal method to establish baseline arterial pressure.i Another group determined that preoperative heart rate variability assessment is an objective and useful instrument for identifying patients with low autonomic physiological reserves and high risk of poor post-operative course.ii Likewise, Reich et al determined that intraoperative tachycardia was associated with adverse outcome in noncardiac surgery.iii Foëx et al found that a preoperative fast heart rate was a harbinger of perioperative adverse cardiac events. Among patients in the INPRESS study who were predominantly undergoing abdominal surgery who were at increased postoperative risk, management targeting an individualized systolic blood pressure, compared with standard management, reduced the risk of postoperative organ dysfunction.iv

We believe safer care can be achieved by focusing on patients in whom ambulatory vital signs indicate severe pathophysiology.

**Objectives**

Using a portable, wireless multi-Vital Sign (VS) monitoring system developed by Caretaker Medical, we have several objectives:

- Primary:
  - Assess the feasibility of placing a Caretaker monitor on subjects scheduled for surgery for an 18-24 hour preoperative ambulatory monitoring session.
  - Assess the feasibility of placing a Caretaker monitor on subjects scheduled for surgery for the perioperative period defined as 18-24 hour intraoperative and postoperative ambulatory monitoring session.
  - Quantitate the data capture rate (estimated at over 99% in the company's prior studies) in this setting and how reliable our monitor return rate is in this setting.
- Secondary:
  - Assess the prevalence of alterations in VS (HR, RR, SaO2, BP, Cardiac Output, Stroke Volume, and HRV preoperatively) in a group of our highest acuity patients (top quartile of risk score) undergoing non-cardiac surgical procedures requiring at least a 2-day admission.
  - Assess any correlation of concerning ambulatory preoperative VS to postoperative VS.
    - We estimate that the percent of time the patient experiences these concerning preoperative VS values will correlate with a higher risk for a similar range of VS postoperatively, as well as undesired outcomes.
      - Undesired outcomes are defined as a) 30-day mortality, b) longer length of stay, c) higher ICU transfer, and 4) RRT calls).

## **Methods and Measures**

### **Design**

The Caretaker device is a wrist device that has a version that has already been approved by the FDA for use amongst medical professionals. For the conduct of this protocol we propose to use a newer version of the device called VitalStream, which has been cleared for use by the FDA.

The New Caretaker device being used in the study has successfully passed all safety and accuracy tests by an independent lab, which have been submitted to the FDA already (see attached Declaration of Conformity).

We plan to monitor ambulatory preoperative CareTaker VS (HR, RR, SaO2, BP, Cardiac Output, Stroke Volume, and HRV) in random patients who meet our inclusion criteria for 18-24 hours, beginning during their preoperative (Preoperative Assessment Clinic, PAC) visit then overnight after they leave. Postoperatively, we will measure these VS in the same patients for approximately 24 hours postoperatively.

These monitors transmit VS to a data cloud, where we will be able to store and then later analyze the VS data. Clinical data will be collected from our EPIC Information System in order to provide pre- and postoperative information to examine corresponding risk factors and provide demographics.

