### **Setting**

The subjects will be recruited in the PAC, where their monitoring period will start, and will continue at their residence (or wherever they decide to stay that night). They will return the monitor with them into the holding area on the day of their surgical procedure. We will replace their monitor on them in the Post-Anesthesia Care Unit (PACU) where it will remain with the patient for 24 hours +/- 6 hours continuously monitoring.

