## **Interventions and Interactions**

*The essential features of interventions and interactions used to generate data for the study should be described.*

- Each participant will have the study summary discussed with them, then allowed to read and sign the informed consent after having the chance to interact with the study equipment and ask questions. This will occur in the PAC prior to their preoperative visit.
- Participants who agree with entering the study will then have the CareTaker monitor placed on their left wrist and calibrated prior to them leaving the PAC.
- No surveys or questionnaires will be administered to subjects.
- An information sheet about the Caretaker device along with an emergency contact number will be given to the study subject at the time the device is placed.
- A description of the monitoring device is located in Appendix B.
- Phase I (preoperative phase) Participants will wear the CareTaker monitor for at least 12 hours (up to 24 hours) in their place of residence during the immediate time period after their initial monitor placement.
- The participants will be asked to remove the monitor and ship it back to us using pre-printed packaging or bring it with them on their day of surgery and admission to the hospital, whichever they prefer.
- For Phase II (intraoperative and postoperative phases) of the study, the participants will then have a monitor placed back on them for intraoperative and postoperative monitoring. The monitor will remain on them for up to 24 hours postoperatively, at which time a member of the research staff will remove the monitor.
- Thus, the total length of time participants will undergo active CareTaker monitoring will be 24-48 hours, divided between pre-and intra- and postoperative phases.
- Participants who complete the entire study will be compensated \$50 for their time and efforts.

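### Postoperative SaO2 is to be correlated with home SaO2 and related to outcomes, but the plan neither records nor accounts for supplemental oxygen

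*Combined protocol and SAP*

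**What the plan says.** Objectives, Design and Outcome Measures all list SaO2 among the monitored vital signs. Preoperative recording is made "in random patients who meet our inclusion criteria for 18-24 hours, beginning during their preoperative (Preoperative Assessment Clinic, PAC) visit then overnight after they leave"; the Setting section adds that it "will continue at their residence (or wherever they decide to stay that night"). For the second period, Design states "Postoperatively, we will measure these VS in the same patients for approximately 24 hours postoperatively", and Setting states "We will replace their monitor on them in the Post-Anesthesia Care Unit (PACU) where it will remain with the patient for 24 hours +/- 6 hours".

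A secondary objective is to "Assess any correlation of concerning ambulatory preoperative VS to postoperative VS". The text under Table 2 repeats this aim for range data and adds the association of ranges with mortality, length of stay, ICU transfer and rapid response calls.

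On covariates, Design offers only a general statement: "Clinical data will be collected from our EPIC Information System in order to provide pre- and postoperative information". The Analytical Plan names a multivariable Cox model without a covariate list. Oxygen therapy, inspired oxygen fraction, home oxygen and CPAP appear neither in the eligibility criteria nor in the data to be collected nor in the analysis. Table 2 gives ranges for heart rate, systolic and diastolic pressure and respiratory rate, and has no SaO2 column.

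**The concern.** Oxygen acts directly on the quantity being measured. It is more likely to be in use in the PACU and ward than at home, and it is often given because saturation is low. The documents give no figures on oxygen use, so these are assumptions, though mild ones.

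The hypothesis in Objectives is that time in a concerning range before surgery goes with time in a similar range afterwards. Oxygen given in response to low saturation moves the patients who would confirm that hypothesis out of the low range. A weak or absent SaO2 correlation could then mean either that home saturation does not predict postoperative saturation or that oxygen therapy worked, and the data as planned could not tell these apart. Any association between postoperative SaO2 and outcomes has the same weakness.

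**Working it through.** **What can be checked from the text.** The plan gives no SaO2 figure to reproduce: no mean, SD, cut-off, expected correlation or share of patients on oxygen. Its one calculation (150 patients) is for heart rate or blood pressure and does not bear on this point. Everything below is illustration with assumed inputs.

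**Direction.** Take PO2 = FiO2 × 713 − PaCO2/0.8 − 10 (sea level, A-a gradient 10 mmHg) and saturation = 100/(1 + 23400/(P³ + 150P)). At PaCO2 60:
- FiO2 0.21: P = 149.7 − 75 − 10 = 64.7, saturation 92.3%.
- FiO2 0.30: P = 213.9 − 75 − 10 = 128.9, saturation 98.9%.

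The same hypoventilation thus gives a different reading. With a fixed gradient this says nothing about shunt.

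**Assumed inputs for size.** Postoperative room-air mean 94%, SD 2.5, true pre-post correlation 0.50, low meaning below 90%. Oxygen either adds L = 2 to 4 points or resets the patient to 97% (SD 1). The cap at 100% is ignored, which changes little.

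**Share below 90%.**
- No oxygen: Φ((90 − 94)/2.5) = Φ(−1.6) = 5.5%.
- All low patients treated, L = 2: Φ(−2.4) = 0.8%. L = 4: Φ(−3.2) = 0.07%. Reset to 97%: essentially 0.
- Half treated at random, L = 2: (5.5 + 0.8)/2, about 3.1%.

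**Correlation, lowest half treated.** The observed r is 0.50 × corr(room-air value, observed value). For a standard normal z, E[z; z < 0] = −0.399.
- Lift L: covariance with z is 2.5 − 0.399L; variance is 6.25 + 0.25L² − 1.995L.
  - L = 2: 1.702/√3.26 = 0.943, so r = 0.47.
  - L = 4: 0.904/√2.27 = 0.600, so r = 0.30.
- Reset to 97%: covariance is 1.25 − 3 × 0.399 = 0.053. The untreated half has mean 94 + 2.5 × 0.798 = 95.99 and variance 6.25 × 0.363 = 2.27. Total variance is 0.5 × 1 + 0.5 × 2.27 + 0.25 × (97 − 95.99)² = 1.89. Then 0.053/√1.89 = 0.039, so r = 0.02.

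**Correlation, oxygen at random to a share p.**
- Reset: r = 0.50(1 − p)2.5/√(6.25(1 − p) + p + 9p(1 − p)), which is 0.34 at p = 0.3 and 0.18 at p = 0.7.
- Lift, p = 0.5: r = 1.25/√(6.25 + 0.25L²), which is 0.46 for L = 2 and 0.39 for L = 4.

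**A second set of inputs.** With means 94 before and 93 after, SD 2, cut-off 92%, 30-90% treated and a lift of 2 or 4 points, a simulation of 400,000 pairs gave r of 0.18-0.48 (targeted) or 0.35-0.48 (random). Postoperative prevalence fell from 30.8% to 0.6-7.5% or 3.7-23.6% respectively. Preoperative prevalence stayed at 15.9% throughout.

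**Does restricting to room-air time repair it?** With the lowest half treated, nobody below 90% remains in the room-air set, so the undercount stays. The correlation recovers only to 0.5 × 0.603/√(0.25 × 0.363 + 0.75) = 0.33. With looser targeting of half the patients it reaches about 0.43, with at most about 0.3% below 90%.

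**Does a composite repair it?** Counting oxygen time or low SaO2 as altered keeps the treated patients in view. If oxygen is routine it overstates: with half on oxygen at random, 0.5 + 0.5 × 0.055 = 53% would count as altered, against 5.5%.

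**The case against.** The case on the other side is substantial, and most of it limits the point without removing it.

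- **Prevalence.** A reader might infer that the prevalence results as a whole are biased. The documents do not support that. The prevalence item ends its list of signs with a reference to the preoperative period and can be read as preoperative only. Oxygen given after surgery cannot alter that figure; only home oxygen or CPAP could.
- **Size.** It is tempting to say that postoperative SaO2 measures oxygen therapy as much as the patient, or that the correlation all but vanishes. Values near zero arise only if oxygen resets treated patients to about 97% whatever their underlying saturation. A lift of 2 to 4 points leaves r at roughly 0.30-0.47. Each calculation also gives a patient one fixed oxygen status, whereas the plan works with percent of time.
- **Definition.** With no SaO2 range in Table 2, low-saturation time is not yet a defined quantity, and the 90% and 92% cut-offs above are assumptions. That is a more basic gap. It does not cure this one, because any cut-off chosen later inherits the problem.
- **Existing data.** The general EPIC collection could include oxygen charting. It is not named, however, and without times the SaO2 minutes cannot be classified. Home use may be impossible to reconstruct later.
- **Consequence.** SaO2 is one sign of seven, in secondary aims of a feasibility study. The primary outcomes are data capture and monitor return. This stands, and sets the weight of the point.

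The clinic accuracy substudy does not answer the concern: it tests whether the device reads correctly, not what the patient is breathing.

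**Conclusion.** The concern holds in limited form. Postoperative SaO2, its correlation with preoperative SaO2 and its association with outcomes are open to bias, because oxygen therapy is neither recorded nor accounted for. The undercount of low-saturation time is the firmer effect: in the first set of inputs, 5.5% falls below 1% whenever oxygen goes to the low patients. The loss of correlation runs in one direction but is of uncertain size, about 0.02 to 0.47 in place of 0.50, and can be small. Both rest wholly on assumed saturation distributions, oxygen effects and treatment patterns.

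The primary outcomes, the HR/BP sample size and preoperative prevalence (home oxygen or CPAP aside) are unaffected. This is a cheap improvement, not a threat to the study's main purpose.

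**What to change.** - **Design:** add to the EPIC extraction the charted oxygen device, flow or FiO2, with times, for the postoperative period. Record home oxygen and CPAP use for Phase I.
- **Analytical Plan:** report postoperative SaO2, and its correlation with preoperative SaO2, by oxygen status (room air and on oxygen), with the share of time on oxygen beside it. Add an analysis in which time on supplemental oxygen or with low SaO2 counts as altered oxygenation. Do not make room-air time the sole primary analysis, since it selects on a treatment given in response to the outcome.
- **Table 2:** add an SaO2 column.
- **Start of the second period:** Setting places the monitor in the PACU, while Interventions and Interactions says "the participants will then have a monitor placed back on them for intraoperative and postoperative monitoring". Reconcile these, so that it is clear which SaO2 time counts as postoperative.

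The cost is one further timed field from a record system already in use, one item asked at the clinic visit and a few sentences of analysis text. The downside is that the composite overstates altered oxygenation where oxygen is routine, which is why it should stand beside the results by oxygen status. Nothing here changes patient care.

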### **Setting**

The subjects will be recruited in the PAC, where their monitoring period will start, and will continue at their residence (or wherever they decide to stay that night). They will return the monitor with them into the holding area on the day of their surgical procedure. We will replace their monitor on them in the Post-Anesthesia Care Unit (PACU) where it will remain with the patient for 24 hours +/- 6 hours continuously monitoring.

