## **Subjects selection criteria**

- **Inclusion Criteria**

- Age > 18 years
- Scheduled for surgery from an outpatient setting and scheduled for a pre-admission PAC appointment
- Risk stratification placing them in the top 25th percentile using our internally-validated PAC Risk Score.

- **Exclusion Criteria**

- Surgery on the day of admission (same-day surgery)
- Any upper extremity surgery

- **Sample Size**

- Our power analysis indicates that we need a total number of 150 patients to have at least 90% power in detecting a change in VS assuming a mean population VS (HR or BP) change of 12% from Phase 1 to Phase 2. We estimate a standard deviation of 10%, a type I error rate (2-sided) of 5%, and 1% missing follow-up data. We may have to consent up to 200 subjects in order to obtain the 150 evaluable subjects.
- We estimate this study lasting up to 12 months.

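### The protocol contradicts itself on whether the Phase II monitor goes on before surgery or in the PACU, so the intraoperative part of a primary objective may go unrecorded; the stated monitoring windows also disagree

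*Combined protocol and SAP*

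**What the plan says.** All references are to the combined protocol and SAP.

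**Sections that include surgery in Phase II**
- Objectives makes it a primary aim to assess feasibility "for the perioperative period defined as 18-24 hour intraoperative and postoperative ambulatory monitoring session".
- Outcome Measure(s) makes capture over the perioperative period the Phase 2 primary outcome. The only definition of that period is the one in Objectives.
- Interventions and Interactions labels Phase II as covering the intraoperative and postoperative phases, has a monitor put back on for both, and divides the total monitoring time between pre-, intra- and postoperative phases.

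**Sections that start Phase II after surgery**
- Setting: "They will return the monitor with them into the holding area on the day of their surgical procedure". It continues: "We will replace their monitor on them in the Post-Anesthesia Care Unit (PACU". As to duration, the PACU is described as the place "where it will remain with the patient for 24 hours +/- 6 hours continuously monitoring".
- Design: "we will measure these VS in the same patients for approximately 24 hours postoperatively". It does not mention recording during surgery.

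**Section that does not settle it.** Table 1 marks the second placement on the day of admission, without saying whether that is before or after the operation.

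**Windows for Phase I.** Objectives asks for feasibility "for an 18-24 hour preoperative ambulatory monitoring session", and Design monitors "for 18-24 hours, beginning during their preoperative (Preoperative Assessment Clinic, PAC) visit then overnight after they leave". Interventions and Interactions sets a 12 h minimum and a 24 h maximum, worn at home. The same section gives 24-48 h as total active monitoring time over all phases.

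**The concern.** Staff cannot follow both Setting and Interventions and Interactions. Under Setting the device is off during the operation, so the intraoperative part of the second primary objective, and of the Phase 2 primary outcome, has nothing to analyse. Recordings that were never made cannot be replaced by any choice of method later.

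If some staff work from one section and some from the other, Phase II will cover surgery in some subjects and not in others. A pooled Phase 2 capture rate would then mix two different quantities.

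There is a smaller knock-on effect for the sample size statement, which assumes "a mean population VS (HR or BP) change of 12% from Phase 1 to Phase 2". That sentence does not define Phase 2. Whether the phase includes time under anaesthesia and surgery changes what the comparison measures.

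The differing windows matter less, but they leave the planned duration of each phase, and the total stated for participants, without a single value.

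**Working it through.** **1. Placement: where is the monitor during surgery?**

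| Section | Phase II start | Surgery recorded? |
|---|---|---|
| Objectives | Not located; session is intraoperative and postoperative | Yes |
| Outcome Measure(s), Phase 2 | Takes the perioperative definition from Objectives | Yes |
| Interventions and Interactions | Not located; placed for both periods | Yes |
| Setting | PACU | No |
| Design | Postoperative | Not mentioned |
| Table 1 | Day of admission | Cannot tell |

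Could the Setting sentence mean exchanging a device that had been worn through surgery? The other text is against it. Table 1 puts the first removal on the day after the clinic visit. Interventions and Interactions has participants take the device off and either ship it or bring it in. Setting has it carried back to the holding area and describes no placement before the PACU. The device is therefore off before the operation.

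With S hours of surgery and a PACU start, intraoperative capture = 0 h / S h = 0% for every S > 0. No assumed length of surgery is needed.

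**2. Windows: does the stated 24-48 h total follow?**

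Inputs, in hours:
- Phase I: 18-24 (Objectives, Design) or 12-24 at home (Interventions).
- Phase II: 18-24 including surgery (Objectives); about 24 postoperative (Design); 24 - 6 = 18 to 24 + 6 = 30 from the PACU (Setting); surgery plus up to 24 postoperative, with no minimum (Interventions).

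Total = Phase I minimum + Phase II minimum, to Phase I maximum + Phase II maximum:

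| Phase I | Phase II | Total (h) |
|---|---|---|
| Objectives/Design | Objectives | 18+18 to 24+24 = 36-48 |
| Objectives/Design | Design | 18+24 to 24+24 = 42-48 |
| Objectives/Design | Setting | 18+18 to 24+30 = 36-54 |
| Interventions | Objectives | 12+18 to 24+24 = 30-48 |
| Interventions | Design | 12+24 to 24+24 = 36-48 |
| Interventions | Setting | 12+18 to 24+30 = 30-54 |
| Interventions | Interventions | 12 + unstated minimum, to 24+24+S = 48+S |

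No pairing gives 24-48 h. The lower end needs 24 - 12 = 12 h as a Phase II minimum, which no section states. The upper end of 48 h, within Interventions and Interactions itself, is 24 + 24 and leaves no room for surgery, although that section counts intraoperative time in the total. The 12 h figure covers wear at home only. Any clinic time adds to it, so sums that use it are lower bounds at their lower end.

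**The case against.** The best defence is that the plan does provide for intraoperative monitoring. Interventions and Interactions, the section that describes procedures, says so in its Phase II label, in its placement step and in its division of total time. A reader who sees only Setting might infer that the study omits surgery by design, or that intraoperative data will certainly be missing. The documents do not support that inference: the loss follows only if Setting is followed. This part of the defence stands, and it makes the point a contradiction between sections. It does not remove the contradiction, because the section that plans intraoperative recording names no place or time for putting the device on, and the one section that does names the PACU.

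The reach is also limited. The secondary correlation is between preoperative and postoperative vital signs, and a PACU start still supplies both. The protocol describes one institution's clinic and record system, so inconsistent practice would arise between staff, not between sites, and it is a possibility rather than a stated fact.

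On the windows, the approximately 24 h in Design and the 24 +/- 6 h in Setting are compatible, since the second can be read as a tolerance on the first. A reader might go further and score recorded hours against a planned window, obtaining capture rates well below or above 100%. The documents do not support that. No section defines capture over a planned window, the 12 h home minimum is not comparable with a window that starts in the clinic, and the time of use named in the Analytical Plan is a usable denominator. What remains is the difference in Phase I minima, whether surgery counts in Phase II, the upper limit of 24 h or 30 h, and a total that does not add up.

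**Conclusion.** The contradiction on placement is real and needs correcting, because it bears on a primary objective and a primary outcome and the loss would be irreversible. Its size is conditional: under the Setting procedure, intraoperative capture is 0% in every subject; under Interventions and Interactions, intraoperative recording is planned. This rests on reading the perioperative period in Outcome Measure(s) as Objectives defines it, which is the only definition given. Phase I capture, the return rate, postoperative capture and the preoperative-to-postoperative correlation are unaffected.

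The disagreement on windows is a lesser matter and would not by itself justify the same priority. It does mean that the stated 24-48 h total cannot be derived from the sections as they stand. The sums with stated minima start at 30 h or more and reach up to 54 h.

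**What to change.** Reconcile Objectives, Design, Setting, Interventions and Interactions, Table 1 and Outcome Measure(s) to one Phase II placement point and one window per phase, and restate the 24-48 h total to match. There are two ways to do this, and the choice is the sponsor's:

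- **Keep intraoperative monitoring.** Change the Setting procedure so that it covers surgery, and have Design and Table 1 say the same. Report capture separately for intraoperative and postoperative time.
- **Drop it.** Remove the intraoperative element from the second primary objective and from the Phase II description, so that the Phase 2 outcome is plainly postoperative.

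The cost is small: wording changes in either case. Keeping intraoperative monitoring also needs a changed placement procedure, some added analysis, and surgery start and end times, which the plan does not list among the data to be collected.
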